### 8.3 Variables

Variable	Role	Data source(s)	Operational definition
Composite of hemorrhagic stroke, ischemic stroke and systemic embolism	Primary effectiveness outcome	HIRA database	
Claims with the following KCD codes in all diagnosis codes (main and sub-diagnosis codes) whichever came first (i.e., the first occurred event will be used):
 

1. Ischemic stroke: G459, I63, I693

2. Systemic embolism: I74

3. Hemorrhagic stroke: I60, I61, I62, I690, I691, I692

 
[NOTE] Hospitalization and CT or MRI codes (brain CT or MRI for ischemic stroke and hemorrhagic stroke; any CT or MRI for systemic embolism) were also required for identification.
 
*Brain CT or MRI:
 
CT: HA441, HA451, HA461, HA471, HA851
 
MRI: HE101, HE102, HE135, HE201,

Variable	Role	Data source(s)	Operational definition
			
HE202, HE235, HE301, HE302, HE401, HE402, HE501, HE502, HE535
 
**Any CT or MRI:
 
CT: HA401, HA402, HA403, HA404, HA405, HA406, HA407, HA408, HA409, HA410, HA411, HA412, HA413, HA414, HA415, HA416, HA424, HA425, HA434, HA435, HA443, HA444, HA445, HA446, HA447, HA448, HA449, HA453, HA456, HA457, HA458, HA459, HA463, HA464, HA465, HA466, HA467, HA468, HA469, HA473, HA474, HA475, HA476, HA477, HA478, HA479, HA496, HA497, HA801, HA805, HA809, HA813, HA834, HA835, HA853, HA856, HA857, HA858, HA859, S4852
 
MRI: HE103, HE104, HE105, HE106, HE107, HE108, HE109, HE110, HE111, HE112, HE113, HE114, HE115, HE116, HE117, HE118, HE119, HE120, HE121, HE122, HE123, HE124, HE125, HE126, HE127, HE128, HE129, HE130, HE131, HE132, HE133, HE134, HE136, HE137, HE138, HE139, HE140, HE141, HE142, HE203, HE204, HE205, HE206, HE207, HE208, HE209, HE210, HE211, HE212, HE213, HE214, HE215, HE216, HE217, HE218, HE219, HE220, HE221, HE222, HE223, HE224, HE225, HE226, HE227, HE228, HE229, HE230, HE231, HE232, HE233, HE234, HE236, HE237, HE238, HE239, HE240, HE241, HE303, HE304, HE305, HE306, HE307, HE308, HE309, HE310, HE311, HE312, HE313, HE314, HE315, HE316, HE317, HE318, HE319, HE320, HE321, HE322, HE323, HE324, HE325, HE326, HE327, HE328, HE329, HE330, HE331, HE332, HE333, HE334, HE403, HE404, HE405, HE406, HE407, HE408, HE409, HE410, HE411, HE412, HE413, HE414, HE415, HE416, HE417, HE418, HE419, HE420, HE421, HE422, HE423, HE424, HE425, HE426, HE427, HE428, HE429, HE430, HE431, HE432, HE433, HE434, HE503, HE504, HE505, HE506, HE507, HE508, HE509, HE510, HE511, HE512, HE513, HE514, HE515, HE516, HE517, HE518, HE519, HE520, HE521, HE522, HE523, HE524, HE525, HE526, HE527, HE528, HE529, HE530, HE531, HE532, HE533, HE534, HE536, HE537, HE538, HE539, HE540, HE541, HF101, HF102, HF104, HF105, HF106, HF107, HF201, HF202, HF305, HF306

Variable	Role	Data source(s)	Operational definition
Individual outcome of primary outcome	Secondary effectiveness outcome	HIRA database	
Claims with the following KCD codes in all diagnosis codes (main and sub-diagnosis codes) whichever came first (i.e., the first occurred event will be used):
 
 
1. Ischemic stroke: G459, I63, I693
 
2. Systemic embolism: I74
 
3. Hemorrhagic stroke: I60, I61, I62, I690, I691, I692
 
 
[NOTE] Hospitalization and CT or MRI codes (brain CT or MRI for ischemic stroke and hemorrhagic stroke; any CT or MRI for systemic embolism) were also required for identification. For CT or MRI codes, please see above.

Major bleeding	Primary safety outcome	HIRA database	
Bleeding requiring hospitalization will be identified using hospital claims which had a bleeding diagnosis code as the first occurred KCD code and it will be consisted of intracranial hemorrhage (ICH) and gastrointestinal (GI) bleeding, and other bleeding. All KCD diagnosis codes (main and sub-diagnosis codes) will be used. Especially, hospitalization and brain CT or MRI codes will be needed to identify ICH.
 
 
- Intracranial (I60, I61, I62, I690, I691, I692, S064, S065, S066, S068)
 
- Gastrointestinal bleeding (I850, I983, K2211, K226, K228, K250, K252, K254, K256, K260, K262, K264, K266, K270, K272, K274, K276, K280, K282, K284, K286, K290, K3181, K5521, K625, K920, K921, K922)
 
- Other bleeding (D62, H448, H3572, H356, H313, H210, H113, H052, H470, H431, I312, N020-N029, N421, N831, N857, N920, N923, N930, N938, N939, M250, R233, R040, R041, R042, R048, R049, T792, T810, N950, R310, R311, R318, R58, T455, Y442, D683)
 

Individual outcome of major bleeding	Secondary safety outcome	HIRA database	
Individual outcome of ICH (diagnosis codes in all main and sub-diagnosis codes + hospitalization + brain CT or MRI), gastrointestinal bleeding (diagnosis codes in all main and sub-diagnosis codes + hospitalization), and other bleeding (diagnosis codes in all main and sub-diagnosis codes + hospitalization).
 
For codes, please see above.

Variable	Role	Data source(s)	Operational definition
Types of health insurance	Covariates	HIRA database	Types of health insurance divided as the following: 1. National Health Insurance 2. Medical aid
CHA 2 DS 2 -VASC	Covariates	HIRA database	CHA 2 DS 2 -VASC as continuous data or dichotomous data. The score will be calculated using the following KCD codes (refer to SAP-Appendix 2, Table 9): 1. Congestive heart failure 2. Hypertension 3. Diabetes mellitus 4. Stroke/TIA/TE 5. Vascular disease 6. Age $\geq$ 75 7. Age 65-74 8. Sex (female)
HAS-BLED	Covariates	HIRA database	HAS-BLED as continuous data or dichotomous data. The score will be calculated using the following KCD codes (refer to SAP-Appendix 2, Table 10): 1. Hypertension 2. Abnormal renal function 3. Abnormal liver function 4. Stroke 5. Bleeding history or predisposition 6. Age $>$ 65 7. Antiplatelet or NSAID use 8. Alcoholism
Charlson Comorbidity Index	Covariates	HIRA database	Charlson Comorbidity Index as continuous data or dichotomous data. The index will be calculated using the following KCD codes (Refer to SAP-Appendix 2, Table 11): 1. Myocardial infarction 2. Congestive heart failure 3. Peripheral vascular disease 4. Cerebrovascular disease 5. Dementia 6. Chronic pulmonary disease 7. Rheumatic disease 8. Peptic ulcer disease 9. Mild liver disease 10. Diabetes without chronic complication 11. Diabetes with chronic complication 12. Hemiplegia or paraplegia 13. Renal disease 14. Any malignancy, including lymphoma and leukemia, except malignant neoplasm of skin 15. Moderate or severe liver disease 16. Metastatic solid tumor 17. AIDS/HIV

Variable	Role	Data source(s)	Operational definition
Medication use	Covariates	HIRA database	
It will be consisted of the following:
 
 
1. History of NSAIDs
 
2. History of antiplatelet
 
3. History of PPI
 
4. History of H2-receptor antagonists
 
5. History of antiarrhythmics
 
6. History of digoxin
 
7. History of statins
 

Exclusion criteria	Exclusion criteria	HIRA database	
Claims with the following KCD codes or procedure codes:
 
 
1. Valvular AF/ Prosthetic heart valves: I05, I08, I09, I34, Q23, T820, T826, Z952, Z953, Z954            - Korean procedure codes: M6580, M6581, M6582, O1791, O1792, O1793, O1794, O1795, O1796, O1797, O1798, O1799, M6531, M6532, M6533, O1690, O1730, 1740, O1750, O1760, O1770, O1781, O1782, O1783, O1810, O1826
 
2. End-stage of chronic kidney disease/dialysis: N185, T824, Y602, Y612, Y622, Y841, Z49, Z992, E1022, E1122, E1222, E1322, E1422
 
3. Kidney transplant: Z940
 
4. Venous thromboembolism: I636, I676, I801, I802, I803, I808, I809, I81, I822, I823, I829, I26
 
5. Hip or knee replacement            - Korean procedure codes: N0711, N0715, N1711, N1715, N1721, N1725, N2070, N2072, N2077, N2710, N2712, N2717, N3710, N3712, N3717, N3720, N3722, N3727, N4710, N4712, N4717, N4720, N4722, N4727
 
6. Thyrotoxicosis: E05
 
7. Pericarditis: I30, I31, I32
 
8. Hypertrophic cardiomyopathy: I422
 
9. Elective defibrillation, radiofrequency ablation, or left atrial appendage occlusion            - Korean procedure codes: M5880, M6540, M6542, M6545, M6547, M6511
 

Follow-up period	Follow-up period	HIRA database	
From the index date until the first occurrence of the following whichever came first:
 
 
1. Discontinuation: maximum of a 30-day gap after the calculated time to finishing the pack based on pack size and number of tablets per day. Switching: switch to any other study drugs
 
2. Outcome occurrence
 
3. Study ends: November 30, 2016
 

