**Table 1. Diagnosis codes for inclusion criteria.**

KCD-6 	KCD-7 
I48 (Atrial fibrillation and flutter)	I48 (Atrial fibrillation and flutter)
I480 (Atrial fibrillation)	I480 (Paroxysmal atrial fibrillation)
I481 (Atrial flutter)	I481 (Persistent atrial fibrillation)
	I482 (Chronic atrial fibrillation)
	I483 (Typical atrial flutter)
	I484 (Atypical atrial flutter)
	I489 (Atrial fibrillation and atrial flutter, unspecified)

KCD-6, Korean version of ICD-10 (6th revision); KCD-7, Korean version of ICD-10 (7th revision)

1) KCD-6 diagnosis codes will be used from 1 July 2015 to 31 December 2015.

2) KCD-7 diagnosis codes will be used from 1 January 2016 to 30 November 2016.

[NOTE] KCD code is based on ICD-10 and almost similar, but KCD code is slightly different from ICD-10 (e.g., ICD-10 is more subdivided and extensive than KCD code).

3. Patients prescribed aspirin, warfarin, or NOACs during intake period (from July 1, 2015 to November 30, 2016)

*[Note] NOACs include apixaban, dabigatran, and rivaroxaban.*

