## 8.7 Data analysis

- All outcome variables will be summarized descriptively through the tabular and graphical display of mean values, medians, ranges, and standard deviations of continuous variables of interest and frequency distributions for categorical variables.
- Patients with aspirin, warfarin, and NOACs will be matched via propensity-score method. Patients will be matched on patient demographics (i.e., age, sex) and clinical (i.e., CHA2DS2-VAsC score, Charlson Comorbidity Index score, etc) variables. Other propensity score method (i.e., covariate adjustment, inverse probability of treatment weighting (IPTW)) will also be used. A Cox proportional hazards model, to account for differences in follow-up time and right data censoring, will be used to compare effectiveness and safety outcomes between treatment groups.
- Comparative analyses will be performed contingent on a feasibility assessment based on the descriptive analyses
- All analyses will be carried out using SAS version 9.4. The 95% confidence intervals for the estimates will be calculated and p < 0.05 considered significant.
- Sensitivity analysis of performing IPTW using the propensity score derived from multinomial model will be conducted.

Detailed methodology for summary and statistical analyses of data collected in this study will be documented in a Statistical Analysis Plan (SAP), which will be dated, filed and maintained by the sponsor. The SAP may modify the plans outlined in the protocol; any major modifications of primary endpoint definitions or their analyses would be reflected in a protocol amendment.

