2.1 STUDY DESIGN

This study will use a retrospective cohort design in which the treatment effectiveness and safety outcomes of new use of NOACs compared to other NOACs, new use of warfarin, and aspirin will be estimated in patients with atrial fibrillation using the Korean Health Insurance Review & Assessment Service (HIRA) database. Comparative analyses will be performed contingent on a feasibility assessment based on the descriptive analyses. Propensity score method and Cox proportional hazards models will be used to account for selection bias, differences in follow-up time, and right data censoring. This will allow us to minimize selection bias and confounding bias and provide outcome data amenable to rapid clinical interpretation (i.e., time-to-event analysis, hazard ratios). Furthermore, HIRA database will allow us to preserve the population-based longitudinal data collection advantages. The overall study design is described in Figure 1.

[figure not shown]

Figure 1. Study design scheme

Study population

Subjects with atrial fibrillation (between January 1, 2007 up to and including the index date*) who newly initiated NOACs, warfarin, or used aspirin between July 1, 2015 and November 30, 2016 in the Korean Health Insurance Review & Assessment Service (HIRA) database.

*Index date is the first prescription date of study drugs, including NOACs, warfarin, and aspirin.

Data source

South Korea has a universal health coverage system that the National Health Insurance covers approximately 97% of the overall South Korean population. The claims data of Health Insurance Review & Assessment Service (HIRA) contains 46 million patients per year that account for 90% of the total population in Korea and include claims from almost 80,000 healthcare service providers across South Korea as of 2011.

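### Stroke sequela codes I690-I693 count as new stroke and intracranial haemorrhage outcomes in any diagnosis position, and no rule ties the imaged admission to a new stroke

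*Protocol*

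**What the plan says.** In Protocol 8.3 the primary effectiveness composite and its individual components use the lists "Ischemic stroke: G459, I63, I693" and "Hemorrhagic stroke: I60, I61, I62, I690, I691, I692". The intracranial part of major bleeding, the primary safety outcome, begins "Intracranial (I60, I61, I62, I690, I691, I692, S064, S065, S066, S068". SAP Appendix 2, Tables 7 and 8, carries the same codes.

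Both documents accept a qualifying code as main or sub-diagnosis. The added filter for stroke in Protocol 8.3 is "Hospitalization and CT or MRI codes (brain CT or MRI for ischemic stroke and hemorrhagic stroke". For intracranial haemorrhage it is likewise an admission and a brain scan. SAP 4.1 describes the events as ones that require hospitalization, but identifies them by a listed code on a hospital claim.

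SAP 5.1 lists one sensitivity analysis: weighting by a propensity score from a multinomial model. The SAP's 3.1 Cohorts text sets out nine pairwise sub-datasets, and SAP 2.1 makes their use conditional: "Comparative analyses will be performed contingent on a feasibility assessment based on the descriptive analyses".

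**The concern.** A sequela code records the late effects of an earlier stroke. It suits a baseline history variable, but it does not by itself show that a new stroke has occurred. Used as an outcome code in any position, it lets an old stroke be counted as an event during follow-up.

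At stake are the primary effectiveness endpoint and the intracranial part of the primary safety endpoint, in every comparison that passes the feasibility step. False events at similar rates in both arms pull hazard ratios toward 1, which hides real differences between drugs. If stroke history stays unbalanced, the bias can go either way. Follow-up stops at the first outcome, so a false event also removes any later true event of that type from that analysis. No planned output would show how many counted events rest on these codes alone.

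**Working it through.** **Step 1: does the rule let an old stroke through?**

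- *Meaning of the code.* Protocol Table 1 notes that "KCD code is based on ICD-10 and almost similar", while adding that the two differ slightly. I69 is the ICD-10 sequelae category. The SAP's own use of the codes is consistent with this: I693 scores prior stroke in Tables 9 and 10, and I690-I692 score bleeding history through Table 8.
- *Position.* A sub-diagnosis is enough.
- *Admission and scan.* Outpatient and unscanned sequela claims do not count. But no rule requires the stroke code to be the reason for admission, an acute code to accompany I69x, or the scan to be linked to the stroke by claim, time or indication.
- *Newness.* Both documents use the first event to occur. That orders events within follow-up; it does not compare them with claims before the index date.
- *Eligibility.* Prior stroke or intracranial haemorrhage is not an exclusion in Protocol 8.2.2 or SAP 3.1. The one overlap with the stroke lists is I636, in the exclusion list that starts "Venous thromboembolism: I636, I676, I801".
- *Start of follow-up.* It begins at the index date, with no blanking period.

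A patient with an old stroke who is admitted for something else, has a brain scan and carries I69x as a sub-diagnosis therefore meets the definition.

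**Step 2: how much could it matter?**

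The plan has no figure to reproduce. Protocol 8.5 gives about 150,000 patients as a database count, with no effect size, event target or power. What follows is an illustration.

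Assumptions: f is the share of reference-arm composite events that are false; false events occur at the same rate in both arms; true HR 0.70; 1:1 allocation; two-sided alpha 0.05; 80% power. The protocol gives only p < 0.05 and 95% intervals.

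- Observed hazard ratio: HR_obs = HR × (1 − f) + f. For f = 0.10: 0.70 × 0.90 + 0.10 = 0.73.
- Events needed: 4 × (1.960 + 0.842)² / (ln HR_obs)². For f = 0 this is 246.8; for f = 0.10 it is 317.0.
- Counted events in a cohort with 246.8 true events: D = 246.8 × (1 + HR_obs) / [(1 − f) × 1.70]. For f = 0.10: 246.8 × 1.73 / (0.90 × 1.70) = 279.0.
- Power in that cohort: Φ(|ln HR_obs| × √D / 2 − 1.960).

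| f | HR_obs | Events needed for 80% power | Counted events D | Power in the same cohort |
|---|---|---|---|---|
| 0 | 0.700 | 247 | 247 | 80.0% |
| 1% | 0.703 | 253 | 250 | 79.5% |
| 5% | 0.715 | 279 | 262 | 77.5% |
| 10% | 0.730 | 317 | 279 | 74.8% |
| 30% | 0.790 | 565 | 371 | 62.2% |

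For a true HR of 0.85 the estimates would be 0.8515, 0.8575, 0.865 and 0.895 at the same four non-zero shares.

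If false events differ between arms by a ratio r, then HR_obs = HR × (1 − f) + f × r. With no true effect (HR = 1) and f = 20%, r = 0.5 gives 0.80 + 0.10 = 0.90, and r = 2 gives 0.80 + 0.40 = 1.20.

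**The case against.** **The meaning of I69 is not printed in the documents.** True. It is, however, the standard title of a category the plan itself uses, and the plan ties KCD to ICD-10.

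**The major bleeding definition refers to the first occurrence of a bleeding code.** This could be read as requiring a code not seen before. The wording is loose, but the more natural reading is first in time during follow-up, and no look-back is described. If a look-back was intended, it needs to be written down.

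**The admission and imaging filter is a real safeguard, and propensity scores balance prior stroke.** Both points stand in part. The filter limits the number of false events. CHA₂DS₂-VASc and HAS-BLED, which score prior stroke, are named propensity covariates with a 0.1 balance threshold, which limits differential error. Balance does not remove false events, so the pull toward 1 remains.

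**Acute codes as sub-diagnoses have the same gap.** An I60-I63 sub-diagnosis is not tied to a new event either. The point here is narrower: an acute code at least denotes an acute stroke, whereas I69x denotes the late effects of an old one.

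**The effect may be trivial.** This stands. Only events that qualify solely through I69x, with admission and brain scan, during on-treatment time in a 17-month window, contribute to f. The rise in events needed also overstates the loss, because counted events rise too; power in the same cohort is the fairer measure.

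**Conclusion.** The outcome definition admits non-events to the primary effectiveness endpoint and to the intracranial part of major bleeding, and the plan has no step that would reveal them. This follows from the code lists and the position rule, taking I69 in its ICD-10 sense.

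The size cannot be derived from the documents. Under equal false rates, the effect is negligible at a 1% share and material from about 10%, where a true HR of 0.70 is estimated as 0.73 and power falls from 80% to about 75%. No figure is claimed for major bleeding, where I690-I692 are three codes in a long list. The definition should be corrected, because the change is small and the error would otherwise stay invisible.

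**What to change.** 1. Remove I690, I691, I692 and I693 from the outcome lists in Protocol 8.3 (composite, individual outcomes, intracranial bleeding) and SAP Tables 7 and 8. I60-I63 remain for acute events.
2. Put I690-I692 in a separate baseline bleeding-history list. HAS-BLED bleeding history in SAP Table 10 points to Table 8, and baseline bleeding in Table 5 follows the major bleeding definition, so both would otherwise lose these codes. The stroke rows of Tables 9 and 10 have their own lists and need no edit. Confirm that the preceding-events variable in Table 3 should follow the shortened lists. The stroke/TIA row of Table 5 states no codes, so give its list explicitly.
3. Report by arm the number of events that qualify only through I690-I693, and keep the present definition as a prespecified sensitivity analysis.

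The cost is the list edits and cross-references, one further run, and a protocol amendment, since Protocol 8.7 says that "any major modifications of primary endpoint definitions or their analyses would be reflected in a protocol amendment". There will be somewhat fewer counted events, and any true event recorded only under I69x is lost from the main analysis. The count and the sensitivity run would show how many events are affected.

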## 1. LIST OF ABBREVIATIONS

Abbreviation	Definition
AIDS	Acquired immune deficiency syndrome
CABG	Coronary Artery Bypass Graft surgery
CHA 2 DS 2 -VASc	Clinical stroke risk prediction tool based on comorbidities of congestive heart failure, hypertension, elderly age, diabetes mellitus, prior stroke or thromboembolism, vascular disease, and gender.
HAS-BLED	Clinical major bleeding risk score based on comorbidities of hypertension, abnormal renal and liver function, prior stroke, bleeding history, labile international normalized ratio values of anticoagulation level, elderly age, and concomitant drug or alcohol use.
HIRA	Health Insurance Review & Assessment Service
HIV	Human immunodeficiency virus
ICD-10	International Classification of Diseases 10 th revision
ICJME	International Committee of Medical Journal Editors
KCD-6	Korean Standard Classification of Diseases 6 th revision
KCD-7	Korean Standard Classification of Diseases 7 th revision
MI	Myocardial infarction
MPR	Medication possession ratio
NOAC	Non vitamin K antagonist oral anticoagulants
NSAIDs	Nonsteroidal anti-inflammatory drugs
NVAF	Nonvalvular atrial fibrillation
OAC	Oral anticoagulants
PCI	Percutaneous coronary intervention

Abbreviation	Definition
PPI	Proton pump inhibitor
TE	Thromboembolism
TIA	Transient ischemic attack

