**Variables:**

Exposure: The exposure to the following will be considered:

1. Aspirin
2. Aspirin-clopidogrel combination\*
3. Clopidogrel\*
4. Warfarin
5. NOACs
  - Apixaban, Rivaroxaban, Dabigtran

\*[Note] Clopidogrel, Aspirin-clopidogrel will be included in descriptive analysis.

Outcome variables: The following outcomes will be assessed:

1. Effectiveness outcomes
  - Primary outcome: Composite of hemorrhagic stroke, ischemic stroke, and systemic embolism
  - Secondary outcomes: Individual outcome of hemorrhagic stroke, ischemic stroke, and systemic embolism
2. Safety outcomes

- Primary safety outcome: Major bleeding including gastrointestinal bleeding or intracranial bleeding and other bleeding
- Secondary safety outcomes: Individual outcome of major bleeding

**Key-Covariates:** Variables, including, but not limited to, will be age, sex, types of health insurance, CHA2DS2-VASc score, HAS-BLED score, Charlson Comorbidity Index score, etc.

**Data sources:** The Korean Health Insurance Review & Assessment Service (HIRA) database from January 1, 2007 to November 30, 2016 will be used for the analysis. The HIRA database contains the data of universal health insurance system in Korea. The database contains patients' demographic information, their use of inpatient and outpatient services, and pharmacy dispensing claims.

**Study size:** Based on HIRA disease statistics, the number of patients with atrial fibrillation (KCD code: I48) were 148,130 and 169,259 in 2015 and 2016, respectively. Thus, the anticipated number of patients will be approximately 150,000 since we plan to include patients who already had atrial fibrillation and were prescribed with aspirin, warfarin, or NOACs from July 1, 2015 to November 30, 2016. However, the study size might change after applying inclusion and exclusion criteria.

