2.2 STUDY OBJECTIVES

Primary objectives

1. To explore baseline characteristics and drug utilization patterns in patients with nonvalvular atrial fibrillation (NVAF) who newly initiated NOACs, warfarin, or used aspirin
 - Demographic and clinical characteristics: Age, sex, types of health insurance, CHA₂DS₂-VASc score, HAS-BLED score, Charlson Comorbidity Index score, etc.
 - Descriptions of index treatment: Types of medication received, index dose intensity
 - Drug utilization pattern: Each patient will be followed-up until the first treatment modification occurs, or study ends (November 30, 2016).
2. To compare effectiveness including hemorrhagic stroke, ischemic stroke and systemic embolism of antithrombotic therapies in patients with NVAF with the following antithrombotic therapies: NOACs, warfarin, and aspirin
 - Primary effectiveness outcome: Composite of hemorrhagic stroke, ischemic stroke, and systemic embolism
 - Secondary effectiveness outcomes: Individual outcome of hemorrhagic stroke, ischemic stroke, and systemic embolism
3. To compare safety of anti-thrombotic therapies in patients with NVAF with the following antithrombotic therapies: NOACs, warfarin, and aspirin
 - Primary safety outcome: Major bleeding including gastrointestinal bleeding or intracranial bleeding and other bleeding
 - Secondary safety outcomes: Individual outcome of major bleeding

[NOTE] comparative analyses will be performed contingent on a feasibility assessment based on the descriptive analyses.

Secondary objectives

1. To explore and understand more detailed drug utilization patterns
 - Standard dose versus reduced dose

- Pattern of usage (i.e., switching, discontinuation) and clinical events preceding the pattern
- Compliance (i.e., medication possession ratio)

2. To compare effectiveness and safety of antithrombotic therapies versus not using therapies among low risk patients (low score of CHA₂DS₂-VASc)

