4 ENDPOINTS AND COVARIATES

4.1 EFFICACY/ EFFECTIVENESS ENDPOINT(S)

Table 1. Effectiveness Endpoints

Variable	Role	Operational definition
Stroke/Systemic embolism	Primary effectiveness outcome	Hemorrhagic stroke, ischemic stroke and systemic embolism requiring hospitalization will be identified using hospital claims which had a hemorrhagic stroke, ischemic stroke or systemic embolism code whichever came first (i.e., the first occurred event will be used). All KCD diagnosis codes (main and sub-diagnosis codes) will be used. Especially, hospitalization and brain CT or MRI codes will be needed to identify ischemic stroke and hemorrhagic stroke. For systemic embolism, hospitalization and any CT or MRI codes will be used (Appendix 2, Table 7).
Individual outcome of primary outcome	Secondary effectiveness outcome	Individual outcome of hemorrhagic stroke (diagnosis codes in all main and sub-diagnosis codes + hospitalization + brain CT or MRI), ischemic stroke (diagnosis codes in all main and sub-diagnosis codes + hospitalization + brain CT or MRI), and systemic embolism (diagnosis codes

Variable	Role	Operational definition
		in all main and sub-diagnosis codes + hospitalization + any CT or MRI)

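### The ischemic stroke code list includes G459, by inference the TIA code, so hospitalized, imaged TIAs would be counted and reported as ischemic stroke

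*Protocol*

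**What the plan says.** The endpoint is named without TIA. SAP 2.2 gives "Primary effectiveness outcome: Composite of hemorrhagic stroke, ischemic stroke, and systemic embolism", and the Protocol abstract has the same three components. The results shell (SAP Table 6) has a single effectiveness row, for stroke and systemic embolism.

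The operational definition is wider. Protocol 8.3 lists "Ischemic stroke: G459, I63, I693" under both the primary composite and the individual outcomes. SAP Appendix 2, Table 7 gives the same three codes. Codes count "in all diagnosis codes (main and sub-diagnosis codes) whichever came first". SAP 4.1 adds that "hospitalization and brain CT or MRI codes will be needed to identify ischemic stroke and hemorrhagic stroke". Under Protocol 8.3, follow-up stops at "Outcome occurrence", among other reasons.

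The plan does use the term TIA elsewhere. The Protocol abbreviation list expands it as "Transient ischemic attack". The CHA₂DS₂-VASc item in Protocol 8.3 is "4. Stroke/TIA/TE", with its codes referred to SAP Table 9. The baseline shell (SAP Table 5) has a joint row for stroke and TIA.

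**The concern.** The endpoint's name and its codes do not match. A reader of the objectives or the results table would take the primary effectiveness result to cover hemorrhagic stroke, ischemic stroke and systemic embolism. The code list also admits an event whose only qualifying code is G459.

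Three things follow if the plan is carried out as written:

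- G459-only admissions enter the primary composite and the ischemic stroke endpoint under the name of stroke.
- Because the first event counts and ends follow-up, a G459 event displaces any later I63 event in the same patient.
- The only analysis listed under Sensitivity Analysis (SAP 5.1; also Protocol 8.7) is weighting from a multinomial propensity model. Nothing planned would show how much of the result rests on G459.

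The individual ischemic stroke endpoint is the more exposed, because hemorrhagic stroke and systemic embolism do not dilute the G459 share there.

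**Working it through.** **1. Is G459 the TIA code?** The documents never print that equation, so it has to be inferred.

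| Place | Label | Codes |
|---|---|---|
| Protocol 8.3 and SAP Table 7, outcome | Ischemic stroke | G459, I63, I693 |
| Protocol 8.3 and SAP Table 4, score item | Stroke/TIA/TE | referred to SAP Table 9 |
| SAP Table 9, CHA₂DS₂-VASc | Stroke | I63, I693, G459 |
| SAP Table 10, HAS-BLED | Stroke | I63, I693, G459 |
| SAP Table 11, Charlson | Cerebrovascular disease | G45.x, G46.x, H34.0, I60.x–I69.x |
| SAP Table 7, outcome | Systemic embolism | I74 |

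The score item must cover TIA, and Table 9 gives it three codes. G459 is not an embolism code in this plan: embolism is I74, and Table 11 groups G45.x with cerebrovascular disease. G459 is thus the only one of the three left to carry TIA. This fits the plan's statement that KCD is based on ICD-10.

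**2. Do the other requirements remove TIA?** No. Hospitalization and a brain CT or MRI code exclude outpatient and unimaged episodes. The imaging code records that a scan was done, not what it showed. No accompanying I63 is required, and Protocol 8.9.1 says charts are not available for validation.

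**3. How far could the HR move?** The plan states no effect size, event count or power, so there is no figure to reproduce. The following is an illustration on assumed inputs:

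- HR_S = 0.70, the HR for stroke/systemic embolism without G459.
- HR_T, the HR for G459-only events: 1.00, 0.85 or 0.70.
- f, the G459-only share of reference-arm events: 10%, 20% or 30%.

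Observed HR = (1 − f) × HR_S + f × HR_T. For example, with f = 0.20 and HR_T = 1.00: 0.80 × 0.70 + 0.20 × 1.00 = 0.76.

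| f | HR_T = 1.00 | HR_T = 0.85 | HR_T = 0.70 |
|---|---|---|---|
| 10% | 0.73 | 0.715 | 0.70 |
| 20% | 0.76 | 0.73 | 0.70 |
| 30% | 0.79 | 0.745 | 0.70 |

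**4. Do the extra events buy precision?** Use Schoenfeld's formula with two-sided 0.05 (assumed), 1:1 allocation and 80% power: D = 4 × (1.96 + 0.84)² / (ln HR)². For HR 0.70 this gives 247 events. The reference arm then holds 247 / 1.70 = 145.3 of them. Adding G459-only events gives a total of 145.3 / (1 − f) × (1 + observed HR). With HR_T = 1.00 this is 279, 320 and 372 events for f = 10%, 20% and 30%, and power is 0.748, 0.689 and 0.622. More events would then go with less power. If instead HR_T = 0.70, the HR is unchanged and the added events raise power. The documents cannot say which case applies.

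**The case against.** The best defence is that this is a consistent, prespecified choice. Protocol and SAP carry the same list, and Tables 9 and 10 use the same three codes under a row labelled simply Stroke. Amendment 02 redefined these outcomes as a substantial change, and Amendment 01 aligned endpoints with a harmonized protocol that is not available here. G459 may come from that source, and removing it could break alignment with it. The hospitalization and imaging requirements also narrow what gets in.

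Much of this stands. The plan pools TIA with stroke wherever it codes it; it does not code TIA as a separate condition. The two documents do not contradict each other. But consistent coding does not cure the label: where the plan wants TIA in a score item or baseline row it names it there, and for the outcome it does not. It also gives no reason for including G459.

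A reader might infer more than the documents support:

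- *That the HR is biased toward 1 and drug differences would be hidden.* This needs treatment to affect G459 events less than stroke. The documents give neither that effect nor the G459 share.
- *That G459 admissions lack an infarct.* Imaging findings are not part of the definition in either direction.
- *That the result would be misread against the randomized trials.* These are cited as background only. No comparison with them is planned, and their endpoint definitions are not in the documents.

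That codes in any diagnosis position qualify applies to I63 as much as to G459, so it is not a separate argument here.

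**Conclusion.** The point holds as a mismatch between the endpoint's name and its codes, affecting the primary composite and the individual ischemic stroke endpoint. It rests on the inference that G459 carries TIA, which is well supported although not printed.

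The numerical consequence is not established. On the assumed inputs, the shift in an HR of 0.70 runs from none to 0.09 (0.70 to 0.79), depending on the G459 share and on the treatment effect on those events. The mislabelling and the absence of any analysis without G459 do not depend on those assumptions. It should be corrected before the comparative results are reported.

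**What to change.** Preferred: remove G459 from the ischemic stroke rows in Protocol 8.3 (composite and individual outcome) and SAP Table 7. Report the composite and the ischemic stroke endpoint with G459 as a sensitivity analysis, labelled stroke/TIA/systemic embolism for the composite and with TIA named likewise for the individual endpoint.

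If inclusion is deliberate, for example for harmonization: state the reason and name TIA in the objectives, endpoint tables and results shells. Prespecify an analysis of both the composite and ischemic stroke without G459.

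Either way, G459 may stay in the baseline stroke/TIA history. SAP Table 3 also draws on Table 7 for the events preceding discontinuation or switching, so say whether G459 still counts there.

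Cost: a protocol and SAP amendment, since Protocol 8.7 requires major changes to primary endpoint definitions to be reflected in one, and one further run of the planned models. Removing the code means somewhat fewer events and slightly wider confidence intervals. Whether power falls depends on the unknown treatment effect on G459 events. Renaming leaves the event count unchanged.
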